### **2.3. Benefit/Risk Assessment**

More detailed information about the known and expected benefits and risks and reasonably expected AEs of zavegepant may be found in the IB, which is the SRSD for this study.

### 2.3.1. Risk Assessment

Potential Risk of Clinical Significance	Summary of Data/Rationale for Risk	Mitigation Strategy
Study Intervention: Zavegepant		
AEs associated with IN administration, such as dysgeusia, throat irritation, nasal congestion and nasal discomfort.	The potential risks are based on AEs reported in studies of zavegepant IN administration, and the majority have been of mild to moderate intensity.	Eligibility criteria have been selected to ensure that only appropriate participants are included in the study (see Section 5). Nasal inspection will be conducted on Screening Visit, Baseline Visit and EOT Visit per the SoA. AEs and clinical laboratory results will be monitored on an ongoing basis.
Use of a placebo arm.	Participants randomized to placebo arm may not experience freedom from pain and freedom from MBS efficacy, as well as freedom from functional disability.	Rescue medication or prescribed standard of care medication is permitted during this study as specified in Section 6.9.2.

### **2.3.2. Benefit Assessment**

The participants may experience improvements during the study and will benefit from more intense monitoring and more frequent assessments compared to usual standard of care. Based on the results of BHV3500-201 and BHV3500-301, participants may benefit from contributing to the understanding of the potential efficacy of zavegepant for the acute treatment of migraine, such as freedom from pain, freedom from MBS, and freedom from functional disability specifically in the Asian population in which little clinical evidence has been collected to date.

Administration of zavegepant was well tolerated at 5 mg, 10 mg, and 20 mg as a single IN spray in adult participants with migraine (BHV3500-201). Zavegepant 10 mg IN was well tolerated in a completed long-term safety study (up to 8 doses per month) in adult participants with migraine for up to 52 weeks (BHV3500-202) and in the completed study of the acute treatment of migraine (BHV3500-301). The most frequently occurring adverse events in clinical studies to date have been primarily associated with IN administration (ie, dysgeusia, throat irritation, nasal congestion, nasal discomfort), and the majority have been of mild to moderate intensity.

Clinical benefit of zavegepant superior to placebo will be further assessed for the acute treatment of migraine in Asian adults in this study, and participants may benefit from the potential efficacy.

### **2.3.3. Overall Benefit/Risk Conclusion**

Taking into account the measures to minimize risk to study participants, the overall benefit-risk profile of zavegepant is favorable. The potential risks identified in association with zavegepant are justified by the anticipated benefits that may be afforded to participants for the acute treatment of migraine.

### 3. OBJECTIVES, ENDPOINTS, AND ESTIMANDS

Objectives	Endpoints	Estimands
Primary:	Primary:	Primary:

 
To compare the efficacy of zavegepant with placebo in the acute treatment of migraine.
 
	
The following co-primary endpoints will be tested:
 
 
Percentage of participants with a pain intensity of none (pain freedom) at 2 hours postdose.
 
Percentage of participants with an MBS reported before dosing that is absent at 2 hours postdose.
 
	
Co-primary estimands:
 
 
The estimand is the treatment effect of zavegepant relative to placebo in terms of the difference in percentage of participants with a pain intensity of none at 2 hours postdose among all randomized participants with migraine headache of moderate or severe intensity who took study intervention. Intercurrent event of taking rescue medication at or before 2 hours postdose will be regarded as a failure.
 
The estimand is the treatment effect of zavegepant relative to placebo in terms of the difference in percentage of participants with an MBS reported before dosing that is absent at 2 hours postdose among all randomized participants with migraine headache of moderate or severe intensity who took study intervention. Intercurrent event of taking rescue medication at or before 2 hours postdose will be regarded as a failure.
 

Secondary:	Secondary:	Secondary:
Key Secondary Objectives:	Key Secondary Endpoints:	Key Secondary Estimands:

 
To compare zavegepant with placebo for measures of early pain relief.
 
	
 
Percentage of participants with a pain intensity of none or mild at 15 minutes postdose.
 
	
 
The estimand is the treatment effect of zavegepant relative to placebo in terms of the difference in percentage of participants with a pain intensity of none or mild at 15 minutes postdose among all randomized participants with migraine headache of moderate or severe intensity who took study intervention. Intercurrent event of taking rescue medication at or before 15 minutes postdose will be regarded as a failure.
 

	
 
Percentage of participants with a pain intensity of none or mild at 30 minutes postdose.
 
	
 
The estimand is the treatment effect of zavegepant relative to placebo in terms of the difference in percentage of participants with a pain intensity of none or mild at 30 minutes postdose among all randomized participants with migraine headache of moderate or severe intensity who took study intervention. Intercurrent event of taking rescue medication at or before 30 minutes postdose will be regarded as a failure.
 

	
 
Percentage of participants with a pain intensity of none or mild at 2 hours postdose.
 
	
 
The estimand is the treatment effect of zavegepant relative to placebo in terms of the difference in percentage of participants with a pain intensity of none or mild at 2 hours postdose among all randomized participants with migraine headache of moderate or severe intensity who took study intervention. Intercurrent event of taking rescue medication at or before 2 hours postdose will be regarded as a failure.
 

Objectives	Endpoints	Estimands

 
To compare zavegepant with placebo for return to normal function.
 
	
 
Percentage of participants with a functional disability level of normal at 2 hours postdose, evaluated for participants with functional disability at the time of dosing.
 
	
 
The estimand is the treatment effect of zavegepant relative to placebo in terms of the difference in percentage of participants with a functional disability level of normal at 2 hours postdose among all randomized participants with migraine headache of moderate or severe intensity who took study intervention and had functional disability at the time of dosing. Intercurrent event of taking rescue medication at or before 2 hours postdose will be regarded as a failure.
 


 
To compare zavegepant with placebo for measures of sustained pain relief.
 
	
 
Percentage of participants with a pain intensity of none or mild at all time points from 2 to 24 hours postdose.
 
	
 
The estimand is the treatment effect of zavegepant relative to placebo in terms of the difference in percentage of participants with a pain intensity of none or mild at all time points from 2 to 24 hours postdose among all randomized participants with migraine headache of moderate or severe intensity who took study intervention. Intercurrent event of taking rescue medication at or before 24 hours postdose will be regarded as a failure.
 

	
 
Percentage of participants with a pain intensity of none or mild at all time points from 2 to 48 hours postdose.
 
	
 
The estimand is the treatment effect of zavegepant relative to placebo in terms of the difference in percentage of participants with a pain intensity of none or mild at all time points from 2 to 48 hours postdose among all randomized participants with migraine headache of moderate or severe intensity who took study intervention. Intercurrent event of taking rescue medication at or before 48 hours postdose will be regarded as a failure.
 

 
To compare zavegepant with placebo for measures of early return to normal function.
 
	
 
Percentage of participants with a functional disability level of normal at 30 minutes postdose, evaluated for participants with functional disability at the time of dosing.
 
	
 
The estimand is the treatment effect of zavegepant relative to placebo in terms of the difference in percentage of participants with a functional disability level of normal at 30 minutes postdose among all randomized participants with migraine headache of moderate or severe intensity who took study intervention and had functional disability at the time of dosing. Intercurrent event of taking rescue medication at or before 30 minutes postdose will be regarded as a failure.
 

	
 
Percentage of participants with a functional disability level of normal at 60 minutes postdose, evaluated for participants with functional disability at the time of dosing.
 
	
 
The estimand is the treatment effect of zavegepant relative to placebo in terms of the difference in percentage of participants with a functional disability level of normal at 60 minutes postdose among all randomized participants with migraine headache of moderate or severe intensity who took study intervention and had functional disability at the time of dosing. Intercurrent event of taking rescue medication at or before 60 minutes postdose will be regarded as a failure.
 

Other Secondary Objectives:	Other Secondary Endpoints:	Other Secondary Estimands:

 
To compare zavegepant with placebo for freedom from individual non-headache associated symptoms of migraine.
 
	
 
Percentage of participants with phonophobia absent at 2 hours postdose, evaluated for participants with phonophobia present at the time of dosing.
 
	
 
The estimand is the treatment effect of zavegepant relative to placebo in terms of the difference in percentage of participants with phonophobia absent at 2 hours postdose among all randomized participants with migraine headache of moderate or severe
 

Objectives	Endpoints	Estimands
		intensity who took study intervention and had phonophobia at the time of dosing. Intercurrent event of taking rescue medication at or before 2 hours postdose will be regarded as a failure.
	
 
Percentage of participants with photophobia absent at 2 hours postdose, evaluated for participants with photophobia present at the time of dosing.
 
	
 
The estimand is the treatment effect of zavegepant relative to placebo in terms of the difference in percentage of participants with photophobia absent at 2 hours postdose among all randomized participants with migraine headache of moderate or severe intensity who took study intervention and had photophobia at the time of dosing. Intercurrent event of taking rescue medication at or before 2 hours postdose will be regarded as a failure.
 

	
 
Percentage of participants with nausea absent at 2 hours postdose, evaluated for participants with nausea present at the time of dosing.
 
	
 
The estimand is the treatment effect of zavegepant relative to placebo in terms of the difference in percentage of participants with nausea absent at 2 hours postdose among all randomized participants with migraine headache of moderate or severe intensity who took study intervention and had nausea at the time of dosing. Intercurrent event of taking rescue medication at or before 2 hours postdose will be regarded as a failure.
 

 
To compare zavegepant with placebo for additional measures of sustained efficacy.
 
	
 
Percentage of participants with a pain intensity of none at all time points from 2 to 24 hours postdose.
 
	
 
The estimand is the treatment effect of zavegepant relative to placebo in terms of the difference in percentage of participants with a pain intensity of none at all time points from 2 to 24 hours postdose among all randomized participants with migraine headache of moderate or severe intensity who took study intervention. Intercurrent event of taking rescue medication at or before 24 hours postdose will be regarded as a failure.
 

	
 
Percentage of participants with a pain intensity of none at all time points from 2 to 48 hours postdose.
 
	
 
The estimand is the treatment effect of zavegepant relative to placebo in terms of the difference in percentage of participants with a pain intensity of none at all time points from 2 to 48 hours postdose among all randomized participants with migraine headache of moderate or severe intensity who took study intervention. Intercurrent event of taking rescue medication at or before 48 hours postdose will be regarded as a failure.
 

	
 
Percentage of participants with pain relapse (any pain intensity above 'none') at any time point after 2 hours postdose, evaluated for participants with pain freedom at 2 hours postdose.
 
	
 
The estimand is the treatment effect of zavegepant relative to placebo in terms of the difference in percentage of participants with a pain intensity of mild, moderate, or severe at any time point after 2 hours postdose among all randomized participants with migraine headache of moderate or severe intensity who took study intervention and had pain freedom at 2 hours postdose. Intercurrent event of taking rescue medication at or before 48 hours postdose will be regarded as a failure.
 

 
To compare zavegepant with placebo for rescue medication use.
 
	
 
Percentage of participants taking rescue medication within 24 hours postdose.
 
	
 
The estimand is the treatment effect of zavegepant relative to placebo in terms of the difference in percentage of participants taking rescue medication within 24 hours postdose among all randomized participants with migraine headache of moderate or
 

Objectives	Endpoints	Estimands
		severe intensity who took study intervention. No relevant intercurrent event is considered since taking rescue medication is the analysis objective.

 
To further compare zavegepant with placebo for early pain relief.
 
	
 
Percentage of participants with a pain intensity of none or mild at 60 minutes postdose.
 
	
 
The estimand is the treatment effect of zavegepant relative to placebo in terms of the difference in percentage of participants with a pain intensity of none or mild at 60 minutes postdose among all randomized participants with migraine headache of moderate or severe intensity who took study intervention. Intercurrent event of taking rescue medication at or before 60 minutes postdose will be regarded as a failure.
 


 
To further compare zavegepant with placebo for early return to normal function.
 
	
 
Percentage of participants with a functional disability level of normal at 15 minutes postdose, evaluated for participants with functional disability at the time of dosing.
 
	
 
The estimand is the treatment effect of zavegepant relative to placebo in terms of the difference in percentage of participants with a functional disability level of normal at 15 minutes postdose among all randomized participants with migraine headache of moderate or severe intensity who took study intervention and had functional disability at the time of dosing. Intercurrent event of taking rescue medication at or before 15 minutes postdose will be regarded as a failure.
 

 
To evaluate the safety and tolerability of zavegepant in the acute treatment of migraine.
 
	
 
Number and percentage of participants with AEs of moderate or severe intensity, SAEs, local irritation AEs, and grade 3 or 4 laboratory test abnormalities.
 
	
 
Not applicable.
 

Tertiary/Exploratory:	Tertiary/Exploratory:	Tertiary/Exploratory:

 
To evaluate the time course of zavegepant efficacy vs placebo.
 
	
 
Percentage of responders at each of the assessed time points (15, 30, 45, 60, 90 minutes; 2, 3, 4, 6, 8, 24, and 48 hours) for each of the primary and secondary endpoints described above that assess a specific time point.
 
	
 
As described above for each primary and secondary endpoint, using the applicable time point.
 

 
To estimate zavegepant relative to placebo for the PGIC ratings.
 
	
 
Percentage of participants with the overall status improvement at 30 minutes, 60 minutes, 2 hours and 24 hours postdose, and the total score of PGIC.
 
	
 
Not applicable.
 

## 4. STUDY DESIGN

### 4.1. Overall Design

This is a Phase 3, randomized, double-blind, placebo-controlled, multicenter, single-attack, outpatient evaluation of the efficacy and safety of zavegepant versus placebo for the acute treatment of migraine in Asian adults. The study intervention is formulated as zavegepant 10 mg IN or matching placebo. The study intervention will be administered using an unidose nasal spray device containing a single dose of zavegepant or matching placebo. The

PFIZER CONFIDENTIAL

CT02-GSOP Clinical Protocol Template Phase 1 2 3 4 (01 April 2022)

Page 35

090177e19cb4b323\Approved\Approved On: 23-Feb-2023 06:46 (GMT)

participants will be instructed to take their study intervention, as an outpatient, if they have a migraine headache which reaches moderate or severe pain intensity.

The total duration of study participation will be up to approximately 16 weeks. This includes a 3-28 day Screening Phase, a Treatment Phase that can last up to 45 days or until the participant has a migraine headache that reaches moderate or severe pain intensity, followed by an EOT Visit 7 (+2) days after the administration of study intervention and a Follow-Up Visit 28-35 days after the administration of study intervention for safety monitoring.

Approximately 1750 participants will be screened to randomize approximately 1400 participants in a 1:1 ratio between the 2 treatment groups (zavegepant or placebo). Before any study procedures are performed, participants must sign informed consent. After informed consent is signed, participants will be enrolled in the IRT system. The participant's migraine history and medical history will be collected at the Screening Visit. Participants will also undergo all screening procedures as indicated in the SoA. Screening Visit must be completed in person.

Within 3-28 days from the Screening Visit, participants will return to the site for the Baseline (Randomization) Visit. Participants who meet all eligibility criteria may be randomized at the Baseline Visit. After randomization is completed in the IRT, study intervention will be dispensed to participants to take home for a single attack of moderate or severe pain intensity occurring up to 45 days after the Baseline (Randomization) Visit. The participants will be provided with an eCOA handheld device. The eCOA handheld device may also be referred to as a handheld or an eDiary. Once a participant experiences a migraine headache of moderate to severe intensity, they should record this in the handheld. The handheld will instruct the participant to take study intervention after the initial assessments are completed in the device. The participant will complete assessments for 48 hours after taking study intervention to record efficacy and other quality of life measures, refer to Section 8.2 Efficacy Assessments for additional information. The study personnel **MUST** instruct and train the participant on the proper use of the handheld to **ENSURE** proper understanding and use of the tool, **PRIOR** to the participant leaving the office at Baseline Visit. Baseline Visit must be completed in person. **Participants in this study may be randomized only once. Under NO circumstances may a participant be re-randomized.**

Participants should be encouraged to treat their **FIRST** qualifying migraine attack (moderate or severe pain intensity) that occurs during the Treatment Phase. If participants are unable to treat their first qualifying migraine, refer to Section 6.9.2 Rescue Medication for a list of medications that are allowed during the course of this study.

Participants will return to the site for EOT Visit (after assessments in the handheld are completed) within 7 (+2) days after administration of study intervention. The "+2" day window is included for scheduling purposes only. Every effort should be made to conduct the EOT Visit within the specified window of 7 (+2) days after administration of study intervention. At the EOT Visit, medication compliance and monitoring of safety assessments will be performed as indicated in the SoA. If a participant has **NOT** treated a migraine attack with study intervention within 45 days after randomization, they are still required to complete

all EOT Visit procedures. All participants must return used and unused study intervention and their handheld device to site. Certain provisions may be implemented, in order to minimize potential hazards to the participants due to COVID-19 **ONLY** at the EOT Visit. These provisions may allow alternatives to in-person study visits and include but are not limited to the following: conducting remote study visits via phone/telemedicine video, focusing on safety assessments during remote visits, performing safety labs via local labs or professional in-home phlebotomy vendors, and shipping of study intervention if needed. Any potential issues should be discussed with sponsor and will be addressed on an individualized basis. Components of the EOT Visit may be conducted under the provisions mentioned above (remote via phone/telemedicine, local labs, etc.), and the window visit may be extended by 5 days due to COVID-19 **ONLY** if circumstances warrant in order to minimize any potential risks to participant safety. Refer to Section 8.3.4.1 and 8.3.5.1 for additional information.

Follow-Up Visit will occur 28-35 days after treatment for safety follow-up of AEs and/or abnormal laboratory tests. Participants may be contacted via telephone. Every effort should be made to conduct the Follow-Up Visit within 28-35 days after treatment. If a participant has NOT treated a migraine attack with study intervention within 45 days after randomization, they are not required to complete the Follow-Up Visit.

## **4.2. Scientific Rationale for Study Design**

The efficacy of zavegepant in the acute treatment of migraine has been demonstrated in BHV3500-201, pivotal, Phase 2/3, double-blind, randomized, placebo-controlled, dose-ranging study of zavegepant 5 mg, 10 mg and 20 mg. This was confirmed in BHV3500-301, a pivotal, Phase 3, double-blind, randomized, placebo-controlled, efficacy and safety study of zavegepant 10 mg. In both trials, zavegepant was administered via intranasal route.

The design of this study will be similar to the pivotal study BHV3500-301. The data from this study will allow characterization of the relative efficacy and safety of zavegepant 10 mg IN versus placebo in the acute treatment of migraine in Asian adults by measuring freedom from pain and freedom from MBS (selected from nausea, photophobia or phonophobia just prior to treatment of the migraine) at 2 hours postdose. Information regarding time to onset of action, sustainability of pain freedom, and freedom from functional disability will also be obtained.

The study intervention is formulated as zavegepant 10 mg IN or matching placebo. The study intervention will be administered using an unidose nasal spray device containing a single dose of zavegepant or matching placebo. The participants will be instructed to take their study intervention, as an outpatient, if they have a migraine headache which reaches moderate or severe pain intensity.

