#### **2.2.2.2. Clinical Efficacy**

In a Phase 2/3, double-blind, randomized, placebo-controlled, dose-ranging study of zavegepant (5 mg, 10 mg, or 20 mg) IN for the acute treatment of migraine (BHV3500-201), zavegepant doses of 10 mg and 20 mg via IN administration demonstrated statistically significant efficacy on both co-primary endpoints of freedom from pain at 2 hours postdose

and freedom from MBS at 2 hours postdose, with little meaningful differences between doses observed. Therefore, the 10 mg dose was selected for further development of intranasal zavegepant for the acute treatment of migraine.

A confirmatory Phase 3 study of zavegepant 10 mg IN administration for the acute treatment of migraine (BHV3500-301) demonstrated statistically significant efficacy for both co-primary endpoints of freedom from pain at 2 hours postdose and freedom from MBS at 2 hours postdose, as well as for 13 of the 17 secondary endpoints tested. These alpha-protected secondary endpoints included measures of ultrarapid onset (eg, pain relief at 15 minutes postdose) and durability of response (eg, sustained pain relief from 2 to 48 hours postdose).

Refer to the IB for more details on the clinical efficacy of zavegepant.

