### 9.1.2. Multiplicity Adjustment

Type I error is controlled by a hierarchical gate-keeping procedure. First, the family of 2 co-primary endpoints is tested. In particular, zavegepant is tested for superiority against placebo at a 2-sided  $\alpha=0.05$  level for both co-primary endpoints. If the tests of both co-

primary endpoints are significant (ie, both p-values are  $\leq 0.05$ ), then the key secondary endpoints are tested hierarchically at the 2-sided alpha=0.05 level in the order shown in Section 3. Thus, a key secondary endpoint is tested only if the preceding key secondary endpoint in the hierarchy is determined to be significant (ie, p-value  $\leq 0.05$ ). If a test in the hierarchy is not significant, then any further tests on endpoints in the sequence will have p-values presented only for descriptive purposes, and no conclusions are drawn from those results.

For other secondary endpoints and exploratory endpoints, no attempt is made to adjust for multiplicity. Any other secondary endpoints and exploratory endpoints for which p-values are produced are evaluated at an unadjusted, 2-sided alpha=0.05 level and presented only for descriptive purposes.

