### 9.5. Sample Size Determination

It is anticipated that about 90% of the 700 participants randomized to each treatment group will have a headache in the allotted time period, resulting in approximately 630 participants evaluable for efficacy in each treatment group.

The sample size calculation is based on pooled efficacy results from the Phase 2/3 BHV3500-201 and Phase 3 study BHV3500-301. The response rates for zavegepant 10 mg and for the placebo group in pooled analysis were 23.2% and 15.1%, respectively, for pain freedom at 2 hours postdose, and 40.5% and 32.1%, respectively, for MBS freedom at 2 hours postdose.

A target sample size of 1260 evaluable participants (630 per group) will provide approximately 95.7% power for the co-primary endpoint of pain freedom at 2 hours postdose, approximately 87.5% power for the co-primary endpoint of MBS freedom at 2 hours postdose, and approximately 84% power to detect a difference between treatment groups for both endpoints jointly, using a 2-sided alpha of 0.05.

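### Sustained pain freedom has no error-controlled test, although its two endpoints could be appended to the fixed sequence without affecting any planned test

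*Protocol*

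**What the plan says.** The rationale in Protocol Section 4.2, repeated in the synopsis and in Section 2.1, rests the evaluation on pain freedom and most bothersome symptom (MBS) freedom at 2 hours, and then adds: "Information regarding time to onset of action, sustainability of pain freedom, and freedom from functional disability will also be obtained".

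Protocol Section 9.1.2 and SAP Section 5.1 test the two co-primaries first. If both succeed, eight key secondaries follow in fixed order, each at 2-sided 0.05:

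1. pain relief at 15 minutes
2. pain relief at 30 minutes
3. pain relief at 2 hours
4. normal function at 2 hours
5. sustained pain relief 2-24 hours
6. sustained pain relief 2-48 hours
7. normal function at 30 minutes
8. normal function at 60 minutes

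Sustained pain freedom appears in Protocol Section 3 under other secondary endpoints, for example "Percentage of participants with a pain intensity of none at all time points from 2 to 24 hours postdose", with a matching 2-48 hour endpoint. For that group Section 9.1.2 states: "For other secondary endpoints and exploratory endpoints, no attempt is made to adjust for multiplicity". Any p-values are judged at an unadjusted 0.05 and are descriptive.

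SAP Sections 6.2.12 and 6.2.13 nevertheless specify response rates, the stratified difference, its 95% confidence interval and a p-value for both endpoints.

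**The concern.** Of the three topics in the quoted sentence, onset and function have an alpha-controlled test and sustained pain freedom does not. The sequence covers durability through sustained pain relief, where none or mild pain counts as success. The pain co-primary requires no pain at all, so the durable version of that outcome has no error-controlled test. Neither document explains the choice.

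At stake is what the report may formally claim. Even a large and precisely estimated difference in sustained pain freedom could be presented only descriptively. In a fixed sequence, tests placed after the last one use no alpha, so leaving these two out protects nothing.

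**Working it through.** **Inputs.** Protocol Section 9.5 plans 630 evaluable participants per arm (700 × 0.90), "using a 2-sided alpha of 0.05". For the 2-hour pain co-primary it states: "The response rates for zavegepant 10 mg and for the placebo group in pooled analysis were 23.2% and 15.1%, respectively, for pain freedom". The MBS freedom rates are 40.5% and 32.1%.

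**Step 1: reproduce the plan's power.** With an unpooled standard error, power = Φ(d/SE − 1.96), where SE = √[(p1(1−p1) + p2(1−p2))/630].

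- Pain freedom: d = 0.081, SE = √[(0.1782 + 0.1282)/630] = 0.02205. Power = Φ(3.673 − 1.960) = 95.7%.
- MBS freedom: d = 0.084, SE = √[(0.2410 + 0.2180)/630] = 0.02699. Power = Φ(3.112 − 1.960) = 87.5%.
- Jointly, as a product: 0.957 × 0.875 = 83.7%, or about 84%.

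All three stated figures reproduce. A pooled null variance gives 95.6% and 87.4%.

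**Step 2: count the endpoints.** Protocol Section 3 lists eight key secondaries and nine other secondary efficacy endpoints: phonophobia, photophobia and nausea freedom; sustained pain freedom 2-24 h and 2-48 h; pain relapse; rescue use; pain relief at 60 minutes; and normal function at 15 minutes. Sustained pain freedom is two of the nine.

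**Step 3: effect of appending two tests on error and on earlier tests.** In a fixed sequence, a false rejection requires rejecting the first true null in the order. That test is done at 0.05, so familywise error is at most 0.05 whatever follows it. The co-primaries and the eight key secondaries are decided before the appended tests are reached, so their rejection probabilities cannot change. Simulation (400,000 runs per setting; correlation 0, 0.5 and 0.8) agrees:

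- Only the two appended endpoints null: familywise error 0.050 to 0.051.
- Key secondary 4 and everything after it null: 0.050 with the eight-test sequence and 0.050 with the ten-test sequence.

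**Step 4: stand-alone power for sustained pain freedom.** The documents give no rates for it. Assumption: the same share r of 2-hour pain-free participants stays pain-free in both arms. Power = Φ[(d − 1.96·SE0)/SE1], with SE0 pooled and SE1 unpooled.

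Worked line for r = 40%: d = 0.0928 − 0.0604 = 0.0324, SE0 = 0.01498, SE1 = 0.01496. Power = Φ[(0.0324 − 0.0294)/0.01496] = Φ(0.203) = 58%.

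| r | zavegepant | placebo | power, 630 per arm |
|---|---|---|---|
| 40% | 9.3% | 6.0% | 58% |
| 50% | 11.6% | 7.6% | 69% |
| 60% | 13.9% | 9.1% | 77% |
| 70% | 16.2% | 10.6% | 84% |
| 80% | 18.6% | 12.1% | 89% |

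**Step 5: power within the sequence.** This is lower, because every earlier test must succeed. The documents give no rates for the eight key secondaries, so any figure is illustrative. One simulated case used correlation 0.5, mean z-values of 3.72 and 3.13 for the co-primaries (close to the planned powers), 3.0 for each key secondary, and 2.5 and 2.2 for the two appended tests. Both co-primaries then succeeded in 86% of runs and all eight key secondaries as well in 50%. Sustained pain freedom was claimed in 44% (2-24 h) and 36% (2-48 h). Weaker key secondaries would lower these figures. Under the plan as written the chance is zero.

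**The case against.** The sponsor's case is reasonable. How many endpoints to make confirmatory is its choice, and here the choice is pre-specified and identical in the protocol and the SAP. Durability already has two alpha-controlled endpoints. Protocol Section 2.2.2.2 itself gives sustained pain relief from 2 to 48 hours as the example of durability in the earlier Phase 3 study. The benefit of appending depends on ten earlier successes. All of this stands and makes the point minor. It does not give a reason to forgo a test that costs nothing, on a stricter outcome than the one in the sequence.

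Four stronger readings are tempting, and the documents do not support them.

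- **That sustained pain freedom is a named purpose of the trial.** The stated purpose is efficacy and safety measured at 2 hours. The quoted sentence promises information, which a descriptive analysis can supply.
- **That no conclusion about it is possible.** Estimates, intervals and p-values are planned. The statement in Section 9.1.2 that no conclusions will be drawn concerns tests in the sequence after a failure. What is missing is an error-controlled conclusion.
- **That the earlier Phase 3 study sets a precedent.** Section 2.2.2.2 reports success "as well as for 13 of the 17 secondary endpoints tested. These alpha-protected secondary endpoints included measures of ultrarapid onset", but it does not list the 17 or say that sustained pain freedom was among them. A similar design does not promise the same hierarchy.
- **That nine unadjusted tests carry a familywise error of 1 − 0.95^9 = 37%.** That figure needs independence and all nulls true. The endpoints overlap: 2-48 hour responders are essentially a subset of 2-24 hour responders. The plan also makes no error-controlled claim from these p-values.

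**Conclusion.** The point holds as a minor, free improvement. As written, both sustained pain freedom endpoints lie outside the alpha-controlled sequence, so the trial cannot support an error-controlled statement on them. Appending them would allow one, with familywise error still at 5% and every planned test unchanged; this part rests on the logic of the procedure and needs no assumed rates.

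The size of the gain does rest on assumptions. Stand-alone power of 58% to 89% supposes equal retention of 40% to 80% in both arms and the planned 2-hour rates. The chance of reaching and passing the appended tests is lower and cannot be fixed from the documents.

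**What to change.** In Protocol Section 9.1.2 (with the ordering in Section 3) and SAP Sections 3.2.1 and 5.1, extend the sequence after return to normal function at 60 minutes. Test sustained pain freedom 2-24 hours and then 2-48 hours, each at 2-sided 0.05 and only if every earlier test is significant. Record the change in SAP Section 2.1, which now lists no modifications. Alternatively, state why the two endpoints stay outside.

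Protocol Section 9 lets the SAP modify the planned analysis and calls for an amendment only for major changes to the primary endpoints or their analyses, so an SAP revision may suffice. The change must precede unblinding. SAP version 2 is dated 28 May 2025, and the documents do not show whether that opportunity remains.

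The cost is a few sentences. No participants, data collection or alpha are needed: pain is already recorded to 48 hours, and the derivations (SAP Appendix 2.1.1) and analyses (SAP 6.2.12 and 6.2.13) already exist. The one consequence to accept is that an appended endpoint that fails is formally reported as not shown.
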